11.6. Appendix 6: Premature Withdrawals & Handling of Missing Data

11.6.1. Premature Withdrawals

Element	Reporting Detail
General	
 Subject study completion was defined as Safety who either prematurely withdrawn or completed FU visits and assessments. Withdrawn subjects were not replaced in the study. All available data from subjects who were withdrawn from the study will be listed and all available planned data will be included in summary tables and figures, unless otherwise specified.

11.6.2. Handling of Missing Data

Element	Reporting Detail
General	
 Missing data occurs when any requested data is not provided, leading to blank fields on the collection instrument: 
 [1] These data will be indicated by the use of a “blank” in subject listing displays. [2] Answers such as “Not applicable” and “Not evaluable” are not considered to be missing data and should be displayed as such.
Outliers	
 Any subjects excluded from the summaries and/or statistical analyses will be documented along with the reason for exclusion in the clinical study report.

11.6.2.1. Handling of Missing Dates

Element	Reporting Detail
General	Partial dates will be displayed as captured in subject listing displays.
Adverse Events	
 The eCRF allows for the possibility of partial dates (i.e., only month and year) to be recorded for AE start and end dates; that is, the day of the month may be missing. In such a case, the following conventions will be applied for calculating the time to onset and the duration of the event: 
 For a missing start day, the 1st of the month will be used unless this is before the start date of investigational product; in this case the study treatment start date will be used (and hence the event is considered On-treatment as per Section 11.3 Appendix 1: Treatment States and Phases). For a missing stop day, the last day of the month will be used, unless this is after the stop date of study treatment; in this case the study treatment stop date will be used. Completely missing start or end dates will remain missing, with no imputation applied. Consequently, time to onset and duration of such events will be missing. Start or end dates which are completely missing (i.e. no year specified) will

Element	Reporting Detail
	remain missing, with no imputation applied.

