11.3.3. Treatment States for AE Data

Treatment State	Definition
AE = Pre-Treatment	AE Start Date < Study Treatment Start Date
AE = On-Treatment	If AE onset date is on or after the treatment start date and on or before the treatment stop date. Study Treatment Start Date ≤ AE Start Date ≤ Study Treatment Stop Date [+ 1]
AE = Post-Treatment	If AE onset date is after the treatment stop date. AE Start Date > Study Treatment Stop Date + 1
AE Onset Time Since 1 st Dose (Days)	If Treatment Start Date > AE Onset Date : = AE Onset Date - Treatment Start Date If Treatment Start Date ≤ AE Onset Date : = AE Onset Date – Treatment Start Date + 1 Missing otherwise
AE Duration (Days)	AE Resolution Date – AE Onset Date + 1
AE = Drug-related	If relationship is marked 'YES' on [Inform/CRF OR value is missing.

NOTES:

- If the study treatment stop date is missing then the AE will be considered to be On-Treatment

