11.6.2.2. Handling of Partial Dates

Element	Reporting Detail
Concomitant Medications	
 Partial dates for any concomitant medications recorded in the CRF will be imputed using the following convention: 
 If the partial date is a start date, a '01' will be used for the day and 'Jan' will be used for the month If the partial date is a stop date, a '28/29/30/31' will be used for the day (dependent on the month and year) and 'Dec' will be used for the month. The recorded partial date will be displayed in listings.
Adverse Events	
 Any partial dates for adverse events will be raised to data management. If the full date cannot be ascertained, the following assumptions will be made: 
 If the partial date is a start date, a '01' will be used for the day and 'Jan' will be used for the month. However, if these results in a date prior to Week 1 Day 1 and the event could possibly have occurred during treatment from the partial information, then the Week 1 Day 1 date will be assumed to be the start date. The AE will then be considered to start on-treatment (worst case). If the partial date is a stop date, a '28/29/30/31' will be used for the day (dependent on the month and year) and 'Dec' will be used for the month. The recorded partial date will be displayed in listings.

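### Two unreconciled SAP rules for partially dated adverse events can give zero or negative durations and can date a Period II event to Period I or to the washout

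*SAP*

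**What the plan says.** SAP 11.6.2.1 states what can be missing: "The eCRF allows for the possibility of partial dates (i.e., only month and year) to be recorded for AE start and end dates". It then gives its rule. Start: "For a missing start day, the 1st of the month will be used unless this is before the start date of investigational product", when the treatment start date replaces it. Stop: "For a missing stop day, the last day of the month will be used, unless this is after the stop date of study treatment". Where month-end is later than that, the imputed stop is capped at the last day of treatment.

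SAP 11.6.2.2 has its own adverse-event row. Partial dates first go to data management. If still unresolved, for the start: "If the partial date is a start date, a '01' will be used for the day and 'Jan' will be used for the month". If that falls before treatment and the event could have occurred during treatment, "then the Week 1 Day 1 date will be assumed to be the start date", which the section calls the worst case. For the stop: "If the partial date is a stop date, a '28/29/30/31' will be used for the day", with December for the month and no treatment cap.

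Neither section refers to the other or names a period, although SAP 11.3.1 defines separate On-Treatment 1 and On-Treatment 2 phases. Neither Time and Events table has a Week 1 Day 1; both number days within Periods I and II. SAP 11.3.3 defines duration as "AE Resolution Date – AE Onset Date + 1". SAP 11.13.7 excludes pre-treatment and washout events from Tables 3.02, 3.03 and 3.04.

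**The concern.** Two paragraphs prescribe how to complete the same field, and for stop dates they give different answers. The cap in 11.6.2.1 suits a trial that stops collecting events at the last dose. Here Protocol 7.4.1.1 collects them to follow-up, so an event can properly start or end after dosing.

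The start rules are written as if there were one treatment start. In a 2 by 2 crossover, moving a date back to the first dose changes more than timing: it can change the treatment to which the event is credited. In sequence PA the first period is placebo, so a Period II event on active drug that is reset to first dosing counts against placebo. If the imputed date falls between the periods, the event leaves Tables 3.02 to 3.04. At stake is which treatment column of those tables, if any, holds a partially dated event.

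**Working it through.** The plan states no figure on this point, so there is none to reproduce. The two rules and the duration formula were applied to illustrative calendars; the calendar dates are assumptions.

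**Stop dates.** Period I 6 to 12 March 2017; Period II 27 March to 2 April 2017, leaving 14 drug-free days. The stop is recorded as April 2017, day missing. 11.6.2.1 gives 2 April, because 30 April is after the last dose. 11.6.2.2, filling only the day, gives 30 April. The last column applies the rule proposed under the fix, assuming last contact on 16 April (14 days after the last dose).

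| Onset | 11.6.2.1 | 11.6.2.2 | Proposed rule |
|---|---|---|---|
| 29 March (Period II Day 3) | 5 | 33 | 19 |
| 3 April (1 day after last dose) | 0 | 28 | 14 |
| 10 April (8 days after) | -7 | 21 | 7 |
| 16 April (14 days after) | -13 | 15 | 1 |

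For example, 2 April - 10 April + 1 = -7, and 30 April - 10 April + 1 = 21. Durations turn negative only when onset is at least 2 days after the capping date. Onset 1 day after gives 0, and earlier onsets are truncated. Since 11.6.2.1 names no period, the cap could also be read as the Period I stop date. An event starting on 28 March with stop recorded as March would then last 12 March - 28 March + 1 = -15 days.

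A second calendar: last dose 30 May, onset 5 June, stop recorded as June. 11.6.2.1 gives 30 May, outside the recorded month, and 30 May - 5 June + 1 = -5. Month-end gives 30 June - 5 June + 1 = 26.

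**Start dates, both periods in one month.** On the March calendar, take a true onset of 28 March (Period II Day 2) recorded as March. The 1st of March precedes first dosing, so both rules return 6 March, Period I Day 1.

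**Start dates, periods in different months.** Period I 13 to 19 February, Period II 11 to 17 March, true onset 12 March recorded as March. 11.6.2.1, and 11.6.2.2 filling only the day, both give 1 March, in the washout.

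**How often.** All 365 Period I start dates in 2017 were run, with onset on each of the seven Period II dosing days and the start day missing. The base is Period II events whose start day is missing. First dosing is taken as Period I Day 1, and the one-day extension in 11.3.3 is not counted.

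| Period II starts, days after last Period I dose | Moved to Period I | Moved to washout | Stays in Period II | Moved to Period I if January is literal |
|---|---|---|---|---|
| 15 | 41% | 46% | 13% | 95% |
| 22 | 18% | 69% | 13% | 93% |
| 31 | 0% | 87% | 13% | 91% |

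The middle three columns are identical for 11.6.2.1 and for 11.6.2.2 filling only the missing day.

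**Size of one event.** With 12 subjects, 1/12 = 8.3 percentage points on a treatment column. SAP 4.1 implies about 11 subjects (10 plus one more); 1/11 = 9.1 points. This assumes that the subject has no other event of that term in the period concerned.

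**The case against.** The strongest objection concerns the start dates. A reader might infer that treatment attribution depends on which paragraph the programmer follows. With Period I 20 to 26 May, Period II 10 to 16 June and a start recorded as June, 11.6.2.1 gives 1 June, and 11.6.2.2 read literally gives 1 January, reset to 20 May. The documents do not support resting the point on that. 11.6.2.1 says only the day can be missing, and 11.6.2.2 tests what is possible from the partial information, so recorded parts count. The natural reading fills only what is missing, and both rules then give 1 June. It follows that moving events into Period I is not peculiar to 11.6.2.2; the flaw is shared. One start conflict survives: an onset month wholly before the first-dose month goes to first dosing under 11.6.2.1 and stays pre-treatment under 11.6.2.2. That case is nearly empty, because AE collection begins with study treatment.

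A reader might also infer that events vanish from the report. They do not. The washout exclusion is noted only for Tables 3.02 to 3.04; Tables 3.05 to 3.08 carry no such note, Listing 12 covers all events, and listings show the date as recorded.

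It is also fair to say that few dates may be affected. Partial dates are queried first, and subjects attend on every dosing day and give PK samples on Days 8 and 9. No AE summary table listed in 11.13.7 reports duration, and safety is descriptive, with no formal analysis. All of this limits the reach. It does not resolve the conflicting stop rules or supply a period-specific start rule for dates that stay partial.

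**Conclusion.** The point holds within limits. The stop rules conflict without precedence, and the cap in 11.6.2.1 can produce zero, negative or truncated durations. The start rules agree in nearly every case on the natural reading, but neither is period-specific. Under either, a Period II event with a missing start day can be placed in Period I or in the washout; literal use of January would make this worse.

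Durations and attributions can be wrong for events whose dates stay partial after query. The documents do not say how many there will be, so it cannot be said that the safety results are wrong. The main consequence is attribution in Tables 3.02 to 3.04, at about 8 to 9 percentage points per event on a treatment column. The percentages by calendar depend on the assumed spacing and on start dates spread evenly over the year. The primary DLco analysis is untouched.

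**What to change.** Replace the two adverse-event paragraphs with one rule that always keeps the recorded month and year.

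- **Missing stop day:** last day of the recorded month, limited to the last contact date and never before onset. No treatment-stop cap.
- **Missing start day:** compare the recorded month, and any known stop date, with the two on-treatment windows in SAP 11.3.1. If the event could have started on treatment in only one period, assign it there, on the first dosing day of that period within the recorded month. If in both, assign it to the active period, in line with the SAP's own worst-case intent, and footnote it. If in neither, use the 1st of the recorded month.
- **Delete** Week 1 Day 1, and the January and December substitutions where the month is known.

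On the examples above, the February and March event goes to 11 March and the May and June event to 10 June, both in Period II. The March event goes to whichever period was active. The rule needs only treatment dates and codes, not a recorded period for each event, which the documents do not show is collected.

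The cost is a paragraph of SAP text and a few lines of derivation code. The downside is a small conservative tilt: an ambiguous placebo event can be counted on active, and an off-treatment onset in a dosing month can be counted as on treatment. Flagging imputed dates in Listing 12 lets a reader see each case.

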11.6.2.2. Handling of Partial Dates

Element	Reporting Detail
Concomitant Medications	
 Partial dates for any concomitant medications recorded in the CRF will be imputed using the following convention: 
 If the partial date is a start date, a '01' will be used for the day and 'Jan' will be used for the month If the partial date is a stop date, a '28/29/30/31' will be used for the day (dependent on the month and year) and 'Dec' will be used for the month. The recorded partial date will be displayed in listings.
Adverse Events	
 Any partial dates for adverse events will be raised to data management. If the full date cannot be ascertained, the following assumptions will be made: 
 If the partial date is a start date, a '01' will be used for the day and 'Jan' will be used for the month. However, if these results in a date prior to Week 1 Day 1 and the event could possibly have occurred during treatment from the partial information, then the Week 1 Day 1 date will be assumed to be the start date. The AE will then be considered to start on-treatment (worst case). If the partial date is a stop date, a '28/29/30/31' will be used for the day (dependent on the month and year) and 'Dec' will be used for the month. The recorded partial date will be displayed in listings.

11.7. Appendix 7: Values of Potential Clinical Importance

11.7.1. Laboratory Values

Haematology				
Laboratory Parameter	Units	Category	Clinical Concern Range	
			Low Flag (< x)	High Flag (>x)
Hematocrit	Ratio of 1	Male		0.54
		Female		0.54
		Δ from BL	↓0.075	
Hemoglobin	g/L	Male		180
		Female		180
		Δ from BL	↓25	
Lymphocytes	x10 ⁹ / L		0.8	
Neutrophil Count	x10 ⁹ / L		1.5	
Platelet Count	x10 ⁹ / L		100	550
White Blood Cell Count (WBC)	x10 ⁹ / L		3	20

Clinical Chemistry				
Laboratory Parameter	Units	Category	Clinical Concern Range	
			Low Flag (< x)	High Flag (>x)
Albumin	mmol/L		30	
Calcium	mmol/L		2	2.75
Creatinine	mmol/L	Δ from BL		↑ 44.2
Glucose	mmol/L		3	9
Magnesium	mmol/L		0.5	1.23
Phosphorus	mmol/L		0.8	1.6
Potassium	mmol/L		3	5.5
Sodium	mmol/L		130	150
Total CO ₂	mmol/L		18	32

Liver Function			
Test Analyte	Units	Category	Clinical Concern Range
ALT/SGPT	U/L	High	≥ 2x ULN
AST/SGOT	U/L	High	≥ 2x ULN
AlkPhos	U/L	High	≥ 2x ULN
T Bilirubin	µmol/L	High	≥ 1.5xULN
T. Bilirubin + ALT	µmol/L U/L	High	1.5xULN T. Bilirubin + ≥ 2x ULN ALT

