9.2. Safety Analyses

9.2.1. Overview of Planned Analyses

The safety analyses will be based on the “All Subjects” population, unless otherwise specified.

Table 5 provides an overview of the planned analyses with further details of data displays being presented in [Appendix 11: List of Data Displays](#).

Table 5 Overview of Planned Safety Analyses

Endpoint	Absolute				Change from Baseline			
	Summary		Individual		Summary		Individual	
	T	F	F	L	T	F	F	L
Exposure								
Extent of Exposure	Y			Y				
Adverse Events								
All AE's ^[1]	Y			Y				
Common AE's	Y							
All Drug-Related AE's	Y			Y				
Serious AE's	Y			Y				
Withdrawal AE's	Y			Y				
C-SSR				Y				
SNAQ				Y				
Audiometry				Y				
Laboratory Values								
Clinical Chemistry ^{[2] [3]}	Y			Y	Y			Y
LFT's	Y			Y				
Hematology /Coagulation ^{[2] [3]}				Y	Y			Y
ECG's								
ECG Findings	Y			Y				
ECG Values					Y			
Vital Signs								
Vitals Values	Y			Y	Y			Y

Endpoint	Absolute				Change from Baseline			
	Summary		Individual		Summary		Individual	
	T	F	F	L	T	F	F	L

NOTES :

- T = Table, F = Figure, L = Listing, Y = Yes display generated.
- Stats Analysis = Represents TFL related to any formal statistical analyses (i.e. modelling) conducted.
- Summary = Represents TFL related to any summaries (i.e. descriptive statistics) of the observed raw data.
- Individual = Represents FL related to any displays of individual subject observed raw data.
- 1. Listings will include subject's numbers for individual AE's & AE system organ classes, preferred terms and verbatim text.
- 2. Chemistry & haematology summaries will include both changes from baseline & results by PCI criteria.
- 3. Listings of chemistry and haematology data for subjects with abnormalities of PCI will be listed.
- 4. Urinalysis summaries will include changes from baseline results by dipstick categories.

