11.8. Appendix 8: Laboratory A&R Dataset Details

Panel ^[1]	Parameter	Unit	Normal Range		Anticipated Direction of Change with Treatment
			Low	High	
Fasted Chemistry	Serum Albumin	G/L	32	50	Safety laboratory parameters not expected to change
	Alkaline Phosphatase	IU/L	20	125	
	ALT	IU/L	0	48	
	AST	IU/L	0	42	
	BUN (UREA)	MMOL/L	2.5	10.5	
	Calcium	MMOL/L	2.12	2.56	
	Chloride	MMOL/L	95	108	
	Creatinine	UMOL/L	67.2	129.1	
	Creatinine Clearance	N/A	N/A	N/A	
	Direct Bilirubin	UMOL/L	0	6	
	GGT	IU/L	0	75	
	Glucose, fasting	MMOL/L	3.9	5.5	
	Potassium	MMOL/L	3.5	5.3	
	Sodium	MMOL/L	135	146	
Lipid	Total Bilirubin	UMOL/L	0	22	Safety laboratory parameters not expected to change
	Total Protein	G/L	60	85	
	Uric Acid	UMOL/L	240	510	
	HDL	MMOL/L	0.9	99.99	
Urinalysis	LDL (Calculated)	MMOL/L	0	3.35	Not able to specify specifically.
	Total Cholesterol	MMOL/L	0	5.15	
	Triglycerides	MMOL/L	0	2.24	
	Blood	Dipstick	N/AP	N/AP	
	Bacteria	Microy	N/AP	N/AP	
	Hyaline Casts (N/A)	N/A	N/AP	N/AP	
	Nitrite	Dipstick	N/AP	N/AP	
	Protein	Dipstick	N/AP	N/AP	
Haematology	RBC	Microscopy	N/AP	N/AP	Safety laboratory parameters not expected to change
	Specific Gravity	N/A	N/AP	N/AP	
	WBC	GI/L	3.8	10.8	
	Basophils	GI/L	0	0.2	
	Eosinophils	GI/L	0.05	0.55	
	Hemoglobin	G/L	118	168	
	Hematocrit	1	0.41	0.5	
	Lymphocytes	GI/L	0.85	4.1	
	MCV	FL	82	103	
	MCH	PG	27	33	
	MCHC	G/L	320	360	
	Monocytes	GI/L	0.2	1.1	

NOTE :

- N/A = Not available on DM dataset during RAP completion.
- N/AP = No ranges are normally provided for parameters.

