11.13.7. Safety Tables

Safety Tables					
No.	Population	IDSL / TST ID / Example Shell	Title	Programming Notes	Deliverable [Priority]
Exposure					
3.01	All Subjects	EX1	Summary of Extent of Exposure		SAC [2]
Adverse Events					
3.02	All Subjects	AE5	Summary of All Adverse Events by System Organ Class	Include total column. Exclude pre-treatment AEs and washout period AEs	SAC [2]
3.03	All Subjects	AE3	Summary of Common Adverse Events by Overall Frequency	AE is considered common if more than one subject experiences it regardless of treatment. Exclude pre-treatment AEs and washout period AEs	SAC [2]
3.04	All Subjects	AE5	Summary of Drug-Related Adverse Events by System Organ Class	Include total column. Exclude pre-treatment and washout period AEs	SAC [2]
3.05	All Subjects	AE1	Summary of Serious Adverse Events by System Organ Class		SAC [2]
3.06	All Subjects	AE1	Summary of Adverse Events Leading to Withdrawals from Study / Permanent Discontinuation of Study Treatment		SAC [2]
3.07	All Subjects	AE15	Summary of Common (>=20%) Non-serious Adverse Events by System Organ Class and Preferred Term		SAC [2]
3.08	All Subjects	AE16	Summary of Serious Adverse Events by System Organ Class and Preferred Term		SAC [2]

Safety Tables					
No.	Population	IDSL / TST ID / Example Shell	Title	Programming Notes	Deliverable [Priority]
Labs					
3.09	All Subjects	LB1	Summary of Clinical Chemistry Laboratory Values by Visit		SAC [2]
3.10	All Subjects	LB1	Summary of Chemistry Changes from Baseline by Visit		SAC [2]
3.11	All Subjects	LB3	Summary of Chemistry Results by Potential Clinical Importance Criteria		SAC [2]
3.12	All Subjects	LB2	Summary of LFTs of Potential Clinical Importance by Visit	Include ALT and total Bilirubin	SAC [2]
3.13	All Subjects	LB1	Summary of Percent Change from Baseline of LFTs by Visit		SAC [2]
3.14	All Subjects	LB1	Summary of Haematology/Coagulation Changes from Baseline by Visit		SAC [2]
3.15	All Subjects	LB17	Summary of Haematology Results by Potential Clinical Importance Criteria		SAC [2]
Vital Signs					
3.16	All Subjects	VS1	Summary of Vital Signs by Visit	Include the Respiration Rate and Temperature	SAC [2]
3.17	All Subjects	VS3	Summary of Change from Baseline in Vital Signs by Visit	Include the Respiration Rate and Temperature	SAC [2]
3.18	All Subjects	VS2	Summary of Vital Signs Results by Potential Clinical Importance Criteria		SAC [2]

Safety Tables					
No.	Population	IDSL / TST ID / Example Shell	Title	Programming Notes	Deliverable [Priority]

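### SAP 11.7.1 labels the creatinine and albumin clinical-concern thresholds in mmol/L, contradicting Appendix 8; if results are converted to that unit, the creatinine flag cannot fire and every albumin value is flagged.

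*SAP*

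**What the plan says.** The clinical chemistry block of SAP 11.7.1 (Values of Potential Clinical Importance, PCI) labels one row "Creatinine mmol/L" and gives albumin the same unit. In full, the two rows read:

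- "Creatinine mmol/L Δ from BL ↑ 44.2", in the high-flag column;
- "Albumin mmol/L 30", in the low-flag column.

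SAP Appendix 8 (section 11.8), which describes the laboratory analysis dataset, gives the same analytes as:

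- "Creatinine UMOL/L 67.2 129.1";
- "Serum Albumin G/L 32 50".

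The 11.7.1 criteria are operative. A note to the safety overview in SAP 9.2.1 says "Chemistry & haematology summaries will include both changes from baseline & results by PCI criteria", and a further note calls for listings of subjects with PCI abnormalities. In the display list, Table 3.11 is the "Summary of Chemistry Results by Potential Clinical Importance Criteria". Listing 20 covers chemistry abnormalities of potential clinical importance, and Listing 22 covers the same as a change from baseline.

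**The concern.** Two appendices of one SAP give different units for the same analytes, and the flag thresholds sit in the appendix whose units do not suit them. A program that honours the printed unit would produce displays that are wrong in opposite directions: no creatinine flag whatever the data show, and an albumin flag for everyone.

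The creatinine side matters more because its failure looks like good news. Creatinine is the only renal marker among the 11.7.1 criteria (urea nitrogen is not there), and its only criterion is this change from baseline. No other clinical chemistry row has a change-from-baseline criterion, so Listing 22 rests on creatinine alone. An empty Listing 22 would read as reassurance. By its programming note, that listing also drops the value and normal-range columns, which removes the context in which a reader might notice the unit.

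**Working it through.** The SAP gives no derivation of 44.2 or 30, so there is no figure to reproduce. The check is a unit conversion against the SAP's own ranges.

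**Inputs**

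| Analyte | Threshold and unit, SAP 11.7.1 | Unit and normal range, SAP Appendix 8 |
|---|---|---|
| Creatinine | rise > 44.2 mmol/L | 67.2 to 129.1 µmol/L |
| Albumin | < 30 mmol/L | 32 to 50 g/L |

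**Creatinine, printed unit applied with conversion**

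- 1 mmol/L = 1,000 µmol/L, so 44.2 × 1,000 = 44,200 µmol/L.
- Against the upper normal limit: 44,200 / 129.1 = 342.
- Against the width of the normal range: 129.1 − 67.2 = 61.9, and 44,200 / 61.9 = 714.
- A rise of that size is not attainable, so the flag cannot fire.

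**Creatinine, number read in the Appendix 8 unit**

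- 44.2 / 67.2 = 66% of the lower limit; 44.2 / 129.1 = 34% of the upper limit.
- That is a reachable rise and a usable flag.

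**Albumin, printed unit applied with conversion**

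This needs a molar mass, which the documents do not give. I assume 66.5 kg/mol, with a range of 60 to 70.

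- 32 / 66.5 = 0.48 mmol/L and 50 / 66.5 = 0.75 mmol/L. Across the assumed range the limits run from 32 / 70 = 0.46 to 50 / 60 = 0.83 mmol/L.
- All of these lie far below 30, so the low flag fires for every subject at every visit.
- The direction does not hang on the assumption. For an albumin of 50 g/L to reach 30 mmol/L, the molar mass would have to be 50 / 30 = 1.67 kg/mol or less.

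**Albumin, number read in the Appendix 8 unit**

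- 30 g/L lies just below the lower normal limit of 32 g/L, which is a usable low flag.

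**Could the label be lost text rather than an error?** Unlikely. The same section prints µmol/L for bilirubin and g/L for hemoglobin, so both units survive there, and a dropped µ could not turn g/L into mmol/L for albumin. All nine rows of the clinical chemistry block carry mmol/L, and for calcium, glucose, potassium and sodium that agrees with Appendix 8. This is what one would see if a single unit had been carried down the column.

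**The case against.** The strongest reply is that this is a labelling slip with no certain effect on any output. The SAP specifies no conversion to the 11.7.1 units. The documented dataset units are those of Appendix 8, and a programmer who compares 44.2 and 30 with those values gets two working flags. If a conversion were made, a table with every albumin value abnormal would be hard to miss, and SAP 11.4.3 provides for a QC spreadsheet. Group-level creatinine values and changes are still summarised by visit in Tables 3.09 and 3.10. All of this stands, and it makes the consequence conditional.

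A reader might also infer that the main laboratory safety outputs are compromised. The display list does not support that. Of the seven laboratory tables, 3.09 to 3.15, only Table 3.11 is touched, and only for two analytes.

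Nor do the documents support the inference that patients are less protected, for example around the saline infusion or intravenous diuretics. The PCI displays are scheduled for the final statistical analysis and trigger no patient management. Protection during the study rests on investigator review of laboratory safety (Protocol 9.4.3), repeat testing of clinically significant abnormal values (Protocol 7.4.9), the stopping criterion for significant changes in safety assessments (Protocol 5.5.3) and ongoing sponsor review (Protocol 9.3.2, SAP 4.1). None of these refers to the 11.7.1 table.

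The objection does not remove the contradiction. The table defines a decision threshold in operative text, and correct output should not depend on a programmer recognising that the specification is wrong.

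**Conclusion.** The two unit labels in SAP 11.7.1 are wrong as written: they contradict Appendix 8, and the threshold values fit only the Appendix 8 units. The consequence depends on the programming.

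- **Printed units applied with conversion:** the creatinine threshold is about 342 times the upper normal limit and cannot be met, Listing 22 is empty, and every albumin value is flagged in Table 3.11 and Listing 20.
- **Numbers applied directly to values in the Appendix 8 units:** both flags behave sensibly.

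A reader might take this to mean that the renal flag has zero sensitivity in all circumstances. The documents show that only under the first reading.

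The scope is two analytes in one end-of-study table and two listings. No endpoint or formal inference is affected, since Protocol 9.4.3 plans no formal analysis of safety data. The creatinine result needs no outside figure. The size of the albumin result rests on the assumed molar mass, but its direction does not. The conclusion that direct application works also assumes that the analysis dataset really holds the Appendix 8 units. Reference ranges come from the local laboratory (Protocol 7.4.9), and the documents do not say in which units results are reported.

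**What to change.** In the unit column of SAP 11.7.1, reconcile the two rows with Appendix 8: creatinine in µmol/L and albumin in g/L. The threshold values stay as they are. Then confirm two things: that the analysis dataset holds both analytes in those units, and that the code for Table 3.11 and Listings 20 and 22 compares like with like.

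The cost is two labels in the SAP and a short programming check. No new data, display or analysis is needed.
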